### **3.9.7 Physical Examination**

Physical examination assessments, if performed, will be shown in a subject listing.

## 4 LIST OF TABLES

Table 14.1.1	Subject Disposition, All Subjects
Table 14.1.2	Demographics and Baseline Characteristics, ITT Population
Table 14.1.3	Demographics and Baseline Characteristics, Per-Protocol Population
Table 14.1.4	Non-Oncological Medical History, ITT Population
Table 14.1.5	Concomitant Medication, ITT Population
Table 14.1.6	Treatment Exposure, ITT Population
Table 14.2.1.1	Progression-free Survival (PFS) Based on RECIST v1.1, Per-Protocol Population
Table 14.2.1.2	Progression-free Survival (PFS) Based on RECIST v1.1, ITT Population
Table 14.2.2.1	Summary of Progression-free Survival (PFS) Based on RECIST v1.1, ITT Population
Table 14.2.2.2	Summary of Progression-free Survival (PFS) Based on irRECIST, ITT Population
Table 14.2.3.1	Summary of Tumor Response, Overall Response Rate and Overall Disease Control Rate Based on RECIST v1.1 Criteria, ITT Population
Table 14.2.3.2	Summary of Tumor Response, Overall Response Rate and Overall Disease Control Rate Based on irRECIST Criteria, ITT Population
Table 14.2.4	Summary of Overall Survival (OS), ITT Population
Table 14.3.1	Summary of Adverse Events, ITT Population
Table 14.3.2	Incidence of Treatment Emergent Adverse Events by MedDRA System Organ Class and Preferred Term, ITT Population
Table 14.3.3	Incidence of Treatment Emergent Adverse Events by MedDRA Preferred Term, ITT Population
Table 14.3.4	Incidence of Treatment Emergent Adverse Events by Maximum CTCAE Grade, MedDRA System Organ Class and Preferred Term, ITT Population
Table 14.3.5.1	Incidence of Treatment Related Adverse Events by MedDRA System Organ Class and Preferred Term, ITT Population
Table 14.3.5.2	Incidence of MEDI4736 Related Adverse Events by MedDRA System Organ

Class and Preferred Term, ITT Population

Table 14.3.5.3	Incidence of Motolimod Related Adverse Events by MedDRA System Organ Class and Preferred Term, ITT Population
Table 14.3.5.4	Incidence of Pegylated Liposomal Doxorubicin (PLD) Related Adverse Events by MedDRA System Organ Class and Preferred Term, ITT Population
Table 14.3.6.1	Incidence of Treatment Related Adverse Events By Maximum CTCAE Grade, MedDRA System Organ Class and Preferred Term, ITT Population
Table 14.3.6.2	Incidence of MEDI4736 Related Adverse Events By Maximum CTCAE Grade, MedDRA System Organ Class and Preferred Term, ITT Population
Table 14.3.6.3	Incidence of Motolimod Related Adverse Events By Maximum CTCAE Grade, MedDRA System Organ Class and Preferred Term, ITT Population
Table 14.3.6.4	Incidence of Pegylated Liposomal Doxorubicin (PLD) Related Adverse Events By Maximum CTCAE Grade, MedDRA System Organ Class and Preferred Term, ITT Population
Table 14.3.7.1	Incidence of Treatment Related Adverse Events Leading to MEDI4736 Withdrawal by MedDRA System Organ Class and Preferred Term, ITT Population
Table 14.3.7.2	Incidence of Treatment Related Adverse Events Leading to Motolimod Withdrawal by MedDRA System Organ Class and Preferred Term, ITT Population
Table 14.3.7.3	Incidence of Treatment Related Adverse Events Leading to PLD Withdrawal by MedDRA System Organ Class and Preferred Term, ITT Population
Table 14.3.8	Incidence of Serious Adverse Events by MedDRA System Organ Class and Preferred Term, ITT Population
Table 14.4.1	Hematology Parameters – Change from Baseline, ITT Population
Table 14.4.2	Hematology Parameters – Shift from Baseline, ITT Population
Table 14.4.3	Chemistry Parameters – Change from Baseline, ITT Population
Table 14.4.4	Chemistry Parameters – Shift from Baseline, ITT Population
Table 14.4.5	Vital Signs – Change from Pre-dose to End of Infusion, ITT Population

Table 14.4.6	ECOG Performance Status at Baseline and Last Assessment, ITT Population
Table 14.4.7	ECG-Shift from Baseline, ITT Population
Table 14.4.8	ECHO or MUGA-Shift from Baseline, ITT Population

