3.1.5 No. of Sites/Subjects

Approximately 6 to 9 sites; and 6 to 53 evaluable subjects are estimated for this study.

Phase 1: 6-18 evaluable subjects will be needed to identify the MTD.

Phase 2: 41 evaluable subjects, including the 6 subjects treated in Phase 1 at the MTD.

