## **1 INTRODUCTION**

LUD2014-001 is an open-label, non-randomized, multicenter Phase 1/2 study of motolimod and MEDI4736 in subjects with recurrent, platinum-resistant ovarian cancer, scheduled to receive pegylated liposomal doxorubicin (PLD). The clinical efficacy and safety of the study drugs in combination will be evaluated during this clinical trial.

Per Amendment 2, motolimod dosing was discontinued for all subjects as of 18 Aug 2016. At the time of Amendment 2, Phase 1 was completed, and Phase 2 was initiated at the +1 dose level (PLD 40 mg/m^2, MEDI4736 1500 mg Q4W). Subjects who initiated treatment prior to August 18, 2016 continued the trial at their respective dose levels for PLD and MEDI4736; however, motolimod was discontinued.

This statistical analysis plan (SAP) contains a detailed description of the data presentations and statistical analyses that will be included in the clinical study report for Protocol LUD2014-001. The statistical methods and analyses described here are based on those presented in the study protocol (Amendment 4 dated 08SEP2017).

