Subjects are enrolled in a non-randomized, competitive multicenter, sequential enrollment manner with central subject registration. Subject enrollment and the safety

of the combination regimen are reviewed on an ongoing basis by an internal data safety monitoring panel.

For each cohort in Phase 1, the start of the Cycle 1 Day 3 study drug administration (MEDI4736 + motolimod) for the first and second subject was separated by at least 24 hours. All subjects' safety data is reviewed for DLTs, before proceeding with a cohort expansion or to a dose-escalated/de-escalated cohort.

Per Amendment 1 (09-DEC-2015), the cohort at dose level 0b was added to Phase 1. Depending on the timing of Amendment 1, dose level 0b cohort could be running concurrently with the cohort at dose level 0a, -1, or +1. Thus, subject enrollment will occur as follows:

- a) When only 1 cohort is open: sequential enrollment;
- b) When 2 parallel cohorts are open: preferential sequential enrollment into the cohort with the higher motolimod dose level or into the cohort with the higher MEDI4736 dose level if both cohorts have the same motolimod dose level.

Subject enrollment is centrally administered.

Enrollment in Phase 2 was initiated after the MTD was established in Phase 1. One patient was enrolled in Phase 2 when motolimod dosing was discontinued for all subjects. The Phase 2 dosing schedule is as follows:

Phase 2 Dosing Schedule	
DAY	CYCLES 1 – 12
1	Pegylated liposomal doxorubicin (IV) 40 mg/m 
3	MEDI4736 (IV) 1500mg

Per Amendment 3 (05-DEC -2016), an optional MEDI4736 treatment extension beyond the initial 12-cycle treatment period (Core Study) was added for subjects who complete the Core Study with Stable Disease or better. The optional treatment extension was permitted for up to 12 additional cycles upon agreement with subject, Sponsor and Investigator, and continued until confirmed disease progression, unless there was unacceptable toxicity, withdrawal of consent, or another discontinuation criterion was met. Under Amendment 4 (08-SEP-2017), the duration of the optional MEDI4736 treatment extension was changed from 12 cycles to “until confirmed disease progression.”

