### **2.2.1 Number of Subjects**

Approximately 6 to 9 sites; and 6 to 53 evaluable subjects were anticipated per the protocol for this study:

Phase 1: 6-18 evaluable subjects to identify the MTD.

Phase 2: 41 evaluable subjects, including the 6 subjects treated in Phase 1 at the MTD.

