## **3.2 Analysis Populations**

### **3.2.1 Intent-To-Treat Population**

The Intent-To-Treat (ITT) Population and the Safety Population are the same for this study and are defined as all subjects who receive at least one dose of PLD, motolimod (pre Amendment 2), or MEDI4736. All tables, listings, and figures will identify this group of subjects as the Intent-to-Treat Population.

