### **3.9.1.4 Treatment Related Adverse Events**

Adverse events with a relationship to study drug of “possibly,” “probably” or “definitely” related will be classified as treatment related.

The number and percentage of subjects who experienced at least one treatment related AE within each specific SOC and PT will be presented overall and by cohort. For the presentation of AE incidences, the SOCs will be sorted alphabetically, and within SOC, the preferred term (PT) will be presented by decreasing total frequency.

The incidences of adverse events related to MEDI4736, motolimod, and PLD will also be summarized by SOC and PT.

Incidence of treatment related AEs will be presented by maximum CTCAE grade for each PT by cohort. For this analysis, if a subject has more than one occurrence of the same PT, then the PT will be counted only once for that subject under the maximum grade at which it was experienced.

The incidences of adverse events related to MEDI4736, motolimod, and PLD will also be presented by maximum CTCAE grade for each PT overall and by cohort.

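### The motolimod-specific adverse event tables use the any-drug ITT denominator, so an overall column that pools the phases would understate motolimod incidence about 2.8 to 2.9 fold at the planned maximum size

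*SAP*

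**What the plan says.** SAP section 3.2.1 makes the ITT and Safety populations the same set, "defined as all subjects who receive at least one dose of PLD, motolimod (pre Amendment 2), or MEDI4736". Receiving motolimod is not required. SAP section 3.9 runs every safety analysis on that set.

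Three tables in SAP section 4 concern motolimod alone, and all are labelled ITT:

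- Table 14.3.5.3, "Incidence of Motolimod Related Adverse Events by MedDRA System Organ Class and Preferred Term, ITT Population".
- Table 14.3.6.3, the same events by maximum CTCAE grade.
- Table 14.3.7.2, related events that led to motolimod withdrawal.

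On columns, SAP section 3.9.1.4 says of the by-grade display that "adverse events related to MEDI4736, motolimod, and PLD will also be presented by maximum CTCAE grade for each PT overall and by cohort". For the display by class and term (Table 14.3.5.3), that section names no columns. Section 3.9.1.5 names none for the withdrawal table.

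On exposure, SAP section 1 states that "motolimod dosing was discontinued for all subjects as of 18 Aug 2016", and SAP section 2.2 that "One patient was enrolled in Phase 2 when motolimod dosing was discontinued for all subjects". The Phase 2 dosing schedule in SAP section 2.2 contains only PLD and MEDI4736. Neither document defines a set of motolimod-treated subjects.

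**The concern.** A subject who never received motolimod cannot have an event caused by it or be withdrawn from it. Such a subject adds to the denominator and never to the numerator. An overall percentage on the ITT set is then not an incidence among people at risk: it mixes the toxicity rate with the share of the trial that enrolled after the drug was stopped.

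The primary objective of Phase 1 is the MTD and safety profile of a combination that then included motolimod. These three tables are the ones devoted to toxicity attributed to that drug. A single overall figure is easily quoted without its cohort breakdown, and it would make motolimod look better tolerated than it was.

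**Working it through.** **Inputs**

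- Total: "6 to 53 evaluable subjects are estimated for this study" (Protocol section 3.1.5).
- Phase 1: "Phase 1: 6-18 evaluable subjects will be needed to identify the MTD" (Protocol section 3.1.5). Every Phase 1 dose level includes motolimod in the SAP dose level table.
- Phase 2: "Phase 2: 41 evaluable subjects, including the 6 subjects treated in Phase 1 at the MTD" (SAP section 2.2.1), so 41 − 6 = 35 are new.
- Early Phase 2 subject: one was enrolled when motolimod stopped. Whether a dose was given is not stated, so let k = 0 or 1.

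**The plan's own figure.** Phase 1 maximum plus Phase 2, less the six shared subjects: 18 + 41 − 6 = 53. This matches the stated maximum.

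**Formulas.** With n subjects in Phase 1:

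- N = n + 35
- exposed = n + k
- unexposed share = (35 − k) / N
- dilution factor = N / (n + k)

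**At the planned maximum, n = 18 and N = 53**

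- k = 1: exposed 19, unexposed 34; 34/53 = 64.2%; 53/19 = 2.79.
- k = 0: exposed 18, unexposed 35; 35/53 = 66.0%; 53/18 = 2.94.

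**Smaller Phase 1 sizes**

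| Phase 1 n | N | Unexposed (k = 1 to k = 0) | Dilution factor (k = 1 to k = 0) |
|---|---|---|---|
| 18 | 53 | 64.2% to 66.0% | 2.79 to 2.94 |
| 15 | 50 | 68.0% to 70.0% | 3.12 to 3.33 |
| 12 | 47 | 72.3% to 74.5% | 3.62 to 3.92 |
| 9 | 44 | 77.3% to 79.5% | 4.40 to 4.89 |
| 6 | 41 | 82.9% to 85.4% | 5.86 to 6.83 |

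**Illustration, with an assumed rate.** If half of the exposed subjects had a motolimod-related event, the pooled overall column at N = 53 would show 0.5 × 19/53 = 17.9% (k = 1) or 0.5 × 18/53 = 17.0% (k = 0), against a rate of 50% among those treated.

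**The case against.** The strongest answer is that the useful rates are already planned. SAP section 3.1.2 presents all data by planned cohort and keeps Phase 1 and Phase 2 apart. Each Phase 1 cohort was assigned motolimod, so its column has essentially the right denominator, and the correct pooled rate can be rebuilt from the cohort counts. This stands: nothing is lost, and the fault is confined to any column that pools exposed with unexposed subjects.

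Second, the same sentence leaves open whether overall in section 3.9.1.4 means both phases together or each phase on its own. Sections 3.9.1.2 and 3.9.1.3 combine all cohorts or subjects for other adverse event tables, so pooling is plausible, but it is not stated for the motolimod tables. If overall is kept within phase, the 2.8 to 2.9 fold figure does not arise.

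Third, ITT is what Protocol section 4.2.2 prescribes for the overall safety analysis. That is true, and it remains right for all-cause and any-drug events. It does not require that the incidence of events attributed to one drug be taken over people who never had that drug.

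A reader might infer more than the documents support:

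- That all three tables are known to carry an overall column. It is explicit only for Table 14.3.6.3.
- That the Phase 2 column is misleading. A near-empty motolimod row in a group scheduled for PLD and MEDI4736 is uninformative, not deceptive.
- That the early Phase 2 subject was exposed. The SAP says only that the subject was enrolled.
- That the dose finding is affected. Protocol section 4.2.2 bases the DLT and MTD assessment on a separate per-protocol set, and no test, dose decision or stopping rule uses these tables.
- That the MEDI4736 and PLD tables need the same change. Both drugs are scheduled for every subject, so no material difference in denominator has been shown.

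**Conclusion.** The concern holds in a limited form. Table 14.3.6.3, and Tables 14.3.5.3 and 14.3.7.2 if they have an all-cohorts column, use a denominator that includes Phase 2 subjects who enrolled after motolimod was stopped. If that column pools the phases, it understates motolimod incidence by a factor of 2.79 to 2.94 at the planned maximum, and by more if Phase 1 enrolled fewer than 18.

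The size rests on three things: planned evaluable numbers, because the actual ITT count is not in the documents and need not equal the evaluable count; pooling across phases; and the unknown exposure of one subject, which is covered by the range. This is a reporting fault in a safety rate. It does not touch the Phase 1 cohort columns or the MTD, but it is worth correcting because the pooled figure answers no useful question.

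**What to change.** Add one sentence to SAP section 3.9.1.4 and repeat it in section 3.9.1.5: for Tables 14.3.5.3, 14.3.6.3 and 14.3.7.2, percentages are based on subjects who received at least one dose of motolimod, by cohort and overall, and the number exposed is shown in each column heading. Change the population label in those three titles to match, and say whether overall combines the phases.

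Showing the exposed number also settles whether the early Phase 2 subject counts, and removes any Phase 1 subject who had PLD on Day 1 but left before the Day 3 motolimod dose. The MEDI4736 and PLD tables stay as they are.

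The cost is one flag derived from dosing records already planned for Table 14.1.6 and Listing 16.2.10, applied to three tables. No new data are needed.

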## 5 LIST OF LISTINGS

Listing 16.2.1	Inclusion or Exclusion Criteria Not Met
Listing 16.2.2	Protocol Deviations
Listing 16.2.3	Study Disposition
Listing 16.2.4	Demographic Characteristics
Listing 16.2.5	Baseline Disease Characteristics
Listing 16.2.6	Non-Oncological Medical History and Procedures
Listing 16.2.7	Prior Oncological Treatment History
Listing 16.2.8	Prior Oncological Radiation History
Listing 16.2.9	Prior Oncological Surgical History
Listing 16.2.10	Study Drug Administration
Listing 16.2.11	Tumor Response by Visit
Listing 16.2.12	CA-125
Listing 16.2.13	Progression-free Survival and Overall Survival
Listing 16.2.14	Prior/Concomitant Medications
Listing 16.2.15	Concomitant Procedures/Surgeries
Listing 16.2.16	Treatment Emergent Adverse Events
Listing 16.2.17	Serious Adverse Events
Listing 16.2.18	Adverse Events Leading to Study Drug Interruption or Discontinuation
Listing 16.2.19	Adverse Events Leading to Study Withdrawal
Listing 16.2.20	Dose-Limiting Toxicities

Listing 16.2.21	Deaths
Listing 16.2.22	Hematology Laboratory Findings
Listing 16.2.23	Chemistry Laboratory Findings
Listing 16.2.24	Abnormal Laboratory Findings
Listing 16.2.25	Vital Signs
Listing 16.2.26	ECOG Performance Status
Listing 16.2.27	ECGs
Listing 16.2.28	ECHO and MUGA
Listing 16.2.29	Physical Examination and Weight

## 6 LIST OF FIGURES

Figure 1.1.1	KM Estimate of Progression-free Survival based on RECIST v1.1, Phase 1 Cohort Dose Level +1 and Phase 2 Combined Per-Protocol Population
Figure 1.1.2	KM Estimate of Progression-free Survival based on RECIST v1.1, Phase 2 Per-Protocol Population
Figure 1.2	KM Estimate of Progression-free Survival based on RECIST v1.1, Phase 1 Cohort Dose Level +1 and Phase 2 Combined Intent-to-Treat Population
Figure 2.1	KM Estimate of Progression-free Survival based on RECIST v1.1 by Cohort, Intent-to-Treat Population
Figure 2.2	KM Estimate of Progression-free Survival based on irRECIST by Cohort, Intent-to-Treat Population
Figure 3	KM Estimate of Overall Survival by Cohort, Intent-to-Treat Population
